Duration of supplemental hydration/feeding (hours) [duration]	Total number of hours of hydration/feeding support experienced from first dose of study drug until end of study (sum of the duration of individual hydration/feeding administration records captured in the Feeding/Supplemental Feeding eCRF) and is derived as: $\text{time hours} = \text{sum} [(\text{end date/time} - \text{start date/time}) \text{ [of encounter]}] / 3600$ Derivation and imputation rules: as for 'Duration of need for intensive care unit (ICU) stay (hours)'
Time (hours) to end of oxygen supplementation up to 72h from first hospital discharge [time to event]	Regardless of whether or not the subject is receiving oxygen supplementation at time of first dose of study drug: time (hours) from first dose of study drug to last end date/time of any oxygen supplementation received, but within 72h following first hospital discharge. Excludes oxygen supplementation received during re-hospitalizations that occurred >72 hours after initial hospital discharge Time (hours) will be set to 0h for subjects not requiring oxygen supplementation after first dose of study drug. Censoring will be applied as follows:

Situation**Censoring**

Table 20: Additional Clinical Course Parameters for Hospitalized Subjects

	
For subjects with missing data prior to event due to:
 
 • Completion • Withdrawal/early discontinuation of the study • Lost to follow-up (LTFU) 
Death (without previous evidence of supplementation end/hospital discharge)
	
Censored at date/time of completion, withdrawal/discontinuation of the study or LTFU accordingly Note: missing time will be imputed as 12:00
 
Censored at date/time of death
				
		time to event (hours) = (date/time of event or censoring – date/time of first dose of study drug)/3600, rounded to one decimal				

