Requirement for Non-invasive Non-mechanical Ventilation Support, Requirement for Non-invasive Mechanical Ventilation Support, Requirement for Invasive Mechanical Ventilation Support

These need for/requirement parameters will be summarized in similar manner as described above and will only be calculated for those subjects that do not require ICU stay or supplemental support (depending on the parameter of interest) before the first dose of study drug.

Time (hours) to End of Oxygen Supplementation, Time (hours) to End of Hydration/Feeding Supplementation, Time (hours) to End of Supplementation (up to 72h from first hospital discharge)

These time to event variables will be analyzed using Kaplan-Meier analysis. Both the 80% and 95% 2-sided confidence intervals will be presented.

The aforementioned will be presented overall by treatment group and by the subgroups as defined in Section 2.4.

In addition, time (hours) to end of oxygen supplementation (up to 72h from first hospital discharge), difference in median time (hours) to event between each active treatment group as compared to placebo will be investigated using the AFT model with log-logistic distribution. The model will include class variables treatment group with placebo as reference and randomization stratification factors (derived). Summary will include parameter estimates and associated standard error, covariance matrix of parameter estimates, estimated accelerated failure time ratio (as compared to placebo) and both 80% and 95% 2-sided confidence intervals.

The aforementioned will be presented overall by treatment group and by the subgroups as defined in Section 2.4.

Graphical presentation will include:

- Overlay of survival curves with Kaplan-Meier survival function and AFT on one plot

- Forest plot of accelerated failure time ratios and resulting confidence intervals for subgroups of interest as defined in Section 2.4 including the relevant subgroup variable as covariate in the model with subgroup*treatment group interaction.

Time to Return to Pre-RSV Disease Level for Respiratory Rate, Time to Return to Pre-RSV Disease Level for Heart Rate, Time to SpO2>92% on Room Air, Time to SpO2>95% on Room Air

These time to event variables will be analyzed using Kaplan-Meier analysis. Both the 80% and 95% 2-sided CIs will be presented.

The aforementioned will be presented overall by treatment group and by the subgroups as defined in Section 2.4.

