
Time (hours) to resolution of RSV [summary parameter] from hospital discharge [time to event]
	
RSV summary parameters:
 
 Key RSV symptoms Overall RSV symptoms 
In the subset of hospitalized subjects (Cohort 1) ‘not resolved’ at date/time of hospital discharge as based on parent/caregiver PRESORS ObsRO: Time (hours) from hospital discharge until the date/time of first observed resolution of all individual RSV concepts comprising the relevant summary parameter (refer to Attachment 2 for concepts comprising each RSV summary parameter). Where resolution is defined as a score of 0 (none) or 1 (mild) for approximately 24h.
 
Utilizing the same derived variables as detailed in Section 5.3.1.2.1:
 
 Time (hours) to resolution Time (hours) to hospital discharge 
time to event (hours) = max(time to resolution [as defined above]) – time to hospital discharge), rounded to one decimal
 
For those subjects ‘resolved’ at date/time of hospital discharge, time (hours) is set to 0h.

Measurement	Formula
Resolved status as based on PRESORS ObsRO: Day 1 to Day 8 [concepts]	
For ObsRO symptoms (concepts): sleep disturbance, crying, illness behavior, breathing problems, retractions, tachypnea, breathing sounds, cough, nasal secretions, tachycardia, feeding, dehydration:
 
Day 1 to Day 8: Resolved status per study day will be categorized as:
 
 • RESOLVED: if individual RSV concept is scored as 0 (none) or 1 (mild) • NOT RESOLVED: if individual RSV concept is scored >1 • MISSING: if no ObsRO assessment for given day (no imputation) 
Note: resolved status will be derived for each study day to Day 21, considering the worst (highest) assessment collected per study day, but is only presented from Day 1 to Day 8.

Resolved status BEFORE/ AFTER HOSPITAL DISCHARGE as based on PRESORS ObsRO [concepts]	
Hospital Discharge: In the subset of hospitalized subjects at time of hospital discharge: for each ObsRO concept, resolved status of the last ObsRO assessment BEFORE hospital discharge/first ObsRO assessment AFTER hospital discharge, will be categorized as described above.

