For the RSV summary parameters specified in Section 5.4.1, these time to event variables will be analyzed using Kaplan-Meier analysis. Both the 80% and 95% 2-sided confidence intervals will be presented.

In addition, the RSV summary parameters will be further explored utilizing a similar AFT model as detailed for time (hours) to resolution in Section 5.3.2.2.

Graphical presentation will include:

- Overlay of survival curves with Kaplan-Meier survival function and AFT on one plot
- Forest plot of accelerated failure time ratios and resulting confidence intervals for subgroups of interest as defined in Section 2.4 including the relevant subgroup variable as covariate in the model with subgroup*treatment group interaction.

The aforementioned will be presented overall by treatment group and by the subgroups as defined in Section 2.4.

Association Between PRESORS: ObsRO: Time (hours) to Resolution: 24h Supplementation Free Definition and Covariates/Baseline Indicators

The potential association between the time (hours) to resolution: 24h supplementation free definition of summary parameter, PRESORS ObsRO: key RSV symptoms and covariates/baseline indicators of interest, as detailed in Section 5.3.2.1, will be explored utilizing a similar AFT model as described in Section 5.3.2.3.2, but including the relevant subgroup variable as covariate in the model with subgroup*treatment group interaction.

PRESORS ObsRO: Sustained Resolution

Proportion (number [n] and percentage [%]) of subjects per individual categories will be presented, as frequency tabulation and graphically, by treatment group. Additionally, 95% 2-sided confidence interval for each binomial proportion within the individual categories will be presented as based on the Wilson score test.

The aforementioned will be presented overall by treatment group and by the subgroups as defined in Section 2.4.

PRESORS ObsRO/ClinRO: Key RSV Symptoms: AUC

With reference to Section 5.2.3, a similar model as used for the primary efficacy analysis at Day 5 will be used for analysis of Day X ($AUC_{Day\ X}$), Day 8 ($AUC_{Day\ 8}$) and additionally for PRESORS ObsRO, Day 10 ($AUC_{Day\ 10}$). Where Day X is defined as the day when at least 50% of Cohort 1 subjects, across all treatment groups, have been discharged from hospital.

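### Time to end of oxygen supplementation is set to 0 h for Cohort 1 subjects needing no oxygen after first dose, but arms are compared with a log-logistic AFT model, which cannot use an event at 0 h

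*SAP*

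**What the plan says.** Table 20 in SAP Section 5.3.1.3.2 takes in every Cohort 1 subject: "Regardless of whether or not the subject is receiving oxygen supplementation at time of first dose of study drug". Its rule for those with no later need is "Time (hours) will be set to 0h for subjects not requiring oxygen supplementation after first dose of study drug". These records are event times, not censored times.

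Section 5.3.2.3.2 plans two analyses. The first is descriptive by arm: "These time to event variables will be analyzed using Kaplan-Meier analysis". The second is the between-arm comparison. It begins "In addition, time (hours) to end of oxygen supplementation (up to 72h from first hospital discharge), difference in median time (hours) to event", and the method is "time (hours) to event between each active treatment group as compared to placebo will be investigated using the AFT model with log-logistic distribution". On covariates: "The model will include class variables treatment group with placebo as reference and randomization stratification factors (derived"). Baseline oxygen status is not among them. The AFT also feeds the subgroup fits, the forest plot and the overlay with the Kaplan-Meier curve.

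A related construction is in Section 5.4.1 (Table 22), time to resolution from hospital discharge. For subjects already resolved at discharge, "time (hours) is set to 0h". Section 5.4.2 then says "the RSV summary parameters will be further explored utilizing a similar AFT model", referring to Section 5.3.2.2, where the distribution is log-logistic.

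**The concern.** A log-logistic AFT model is a linear model for log time, and the logarithm of zero does not exist. Neither section gives an offset, a two-part model, interval censoring or an exclusion rule for the 0 h records, so the specified comparison cannot be run on the specified variable. The program will stop, drop the records, or run on a substitute value chosen by the analyst, and these routes give different answers.

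At stake is the only planned between-arm estimate of time on oxygen. If the zeros are dropped, the ratio no longer compares the randomized arms in full, and the overlay plot sets a Kaplan-Meier curve for all subjects beside an AFT curve for some of them.

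**Working it through.** **1. The plan's own AFT figure.** Section 1.4 gives, for Cohort 1 symptom resolution, medians of 3 and 2 days, scale parameter 1/0.65, 48 per arm, and 95% probability of an effect in the right direction. Read as shape 1/0.65 (σ = 0.65):
- SE = 0.65 × √3 × √(2/48) = 0.230; |ln(2/3)| = 0.405; Φ(0.405/0.230) = 96.1%.
- With the SE of mean log time, 0.65 × (π/√3) × √(2/48) = 0.241, the result is 95.4%.

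The figure reproduces. Taking σ = 1/0.65 gives only 76–77%. The SAP states no figure for the oxygen endpoint.

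**2. The likelihood near 0 h.** With median a and shape b, ln f(t) = ln(b/a) + (b−1) ln(t/a) − 2 ln(1 + (t/a)^b). For a = 72 h:
- b = 1/0.65: −6.15 at 1 h, −9.87 at 0.001 h, −21.03 at 10⁻¹² h, tending to minus infinity.
- b = 0.8: −3.71, −2.26 and +1.88 at the same times, tending to plus infinity.

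An event at exactly 0 h therefore has no usable contribution.

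**3. Who has 0 h.** Subjects still on oxygen after first dose have positive times. Zeros come from subjects off oxygen at first dose who do not need it later, including any who stopped before first dose. Treatment can change the zero share only by preventing new oxygen need.

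**4. Precision if zeros are dropped.** With a share q of zeros in each arm, n per arm is 48(1−q). Borrowing the inputs of step 1, the 96.1% becomes 94.3% at q = 20% (n = 38.4) and 89.4% at q = 50% (n = 24).

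**5. Bias if zeros are dropped.** Simulation with 48 per arm, 400 runs, σ = 0.65 and a placebo user median of 48 h. The median and all zero shares are assumptions. Active spares some subjects oxygen and leaves all other durations unchanged. Fitted time ratio, active to placebo:

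| Zeros, placebo / active | Mildest cases spared | Duration unrelated to who is spared |
|---|---|---|
| 30% / 30% | 1.00 | 0.98 |
| 30% / 40% | 1.28 | 0.97 |
| 30% / 50% | 1.57 | 0.99 |
| 50% / 60% | 1.40 | 1.02 |
| 50% / 70% | 1.99 | 1.00 |

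If active also shortens users' times by one third, the ratio is 0.67 with equal shares (30% / 30%), as it should be, and 1.11 with 30% / 50% and the mildest spared.

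**6. A milder set of assumptions.** Suppose 40–60% are off oxygen at dosing, new need is 10–20% on placebo and half that on active, and duration is unrelated to who is spared. A true ratio of 0.67 is then estimated at 0.65–0.67. Linking duration to who is spared would add bias.

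**7. Substituting a small value.** For 30% / 50% with the mildest spared, replacing 0 h by 0.1, 1 or 6 h gives ratios of 0.27, 0.51 and 0.81. The substitute sets the answer.

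**8. The discharge endpoint.** Table 22 limits it to Cohort 1 subjects not resolved at discharge, then assigns 0 h to those who are resolved. The two statements conflict. If the 0 h records stay, they cannot enter the AFT of Section 5.4.2.

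**The case against.** The strongest reply is that the harm is narrow and may be small.
- **The restriction is inferred.** A reader might conclude that the SAP limits this comparison to a post-randomization subset. It does not say so; that is what follows if zeros are dropped, and a failed fit is equally possible. Membership is fixed by baseline status for subjects on oxygen at first dose. This stands.
- **Oxygen avoidance is assessed elsewhere.** A reader might infer that any benefit from avoiding oxygen is lost. Section 5.3.2.3.2 compares need for oxygen by a stratified risk difference in subjects not requiring it before first dose. The RSV Recovery Scale and clinically resolved status also count oxygen need, and Kaplan-Meier keeps the zeros. This stands, but none of it repairs the time ratio.
- **Large biases need large effects on new oxygen need.** Gaps of 10 to 20 points across a whole arm have no support in the SAP, and step 6 shows little bias under milder inputs. This stands against quoting any one magnitude, but not against the point that the model cannot be run as specified.
- **The discharge endpoint is not simply a second instance.** Its restriction is written, and its clock starts at discharge, itself a post-randomization event, so keeping zeros would not cure it. This stands.
- **The endpoint carries little formal weight.** It is secondary and confined to Cohort 1. It is not one of the three key clinical course endpoints, and no MCP-Mod test is planned on it. This stands and lowers the severity.

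**Conclusion.** The point holds in a limited form. The definition and the model are incompatible for every 0 h record, and this does not depend on any assumption. Everything about size does, because the SAP gives no zero share. If zeros are dropped, there is no bias when the shares are equal. When active prevents new oxygen need, the ratio can move to 1 or past it, to between 1.28 and 1.99 in the assumed cases where the mildest are spared and other durations are unchanged.

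The defect is confined to the oxygen AFT with its subgroup fits, forest plot and overlay. The feeding/hydration and combined supplementation endpoints also take 0 h but have only Kaplan-Meier planned. A reader might infer a threat to the primary viral load analysis or the interim decisions; the endpoint enters neither, nor the alpha scheme of Section 5.2.3.2. Severity is moderate.

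**What to change.** In Section 5.3.2.3.2, make the between-arm comparison for time to end of oxygen supplementation the difference in restricted mean time from the planned Kaplan-Meier curves, with zeros kept. State the restriction time in advance, adjust for the derived stratification factors, and give 80% and 95% CIs.

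Keep the log-logistic AFT, with its forest plot and overlay, as supportive only, in subjects on oxygen at first dose. That subset is defined at baseline; label the output accordingly and draw the overlaid Kaplan-Meier curve in the same subset.

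Separately, reconcile Table 22 on time to resolution from hospital discharge: either resolved subjects are outside the endpoint or they count as 0 h. If they count, they cannot enter the AFT of Section 5.4.2. Because the clock starts at discharge, label this result descriptive in either case.

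The cost is SAP wording and some programming, with no new data. The loss is a time ratio for the full Cohort 1. The wording should be settled before unblinded results on this endpoint are used, since the handling of zeros can change the direction of the estimate.

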Actual duration of intensive care unit (ICU) stay (hours) [duration]	
For subjects in Cohort 1: total number of hours of actual ICU stay experienced by a subject from first dose of study drug until end of study (sum of the duration of individual ICU records captured in the Hospitalization [Inpatient] eCRF) and is derived as:
 
time hours = sum [(end date/time – start date/time [of encounter])]/3600
 
Derivation and imputation rules: as for 'Duration of need for intensive care unit (ICU) stay (hours)'

Table 20: Additional Clinical Course Parameters for Hospitalized Subjects

Need for ICU stay [binary]	
Was there a medical need for the subject to stay in the ICU after first dose of study drug? Categories will be Yes (1) or No (0).
 
Only derive this parameter for subjects that were not in ICU before first dose of study drug (no score will be assigned otherwise).

Duration of oxygen supplementation [duration]	
The total number of hours a subject used supplemental oxygen (=event) from first dose of study drug until study termination, calculated as sum of [(end date/time of event - start date/time of event)/3600], rounded to one decimal for all separate events per subject
 
Derivation and imputation rules: as for 'Duration of need for intensive care unit (ICU) stay (hours)'
 
If the subject required oxygen supplementation prior to the current respiratory infection, the end date/time will be the date/time that the supplemental oxygen administration returned to the level provided prior to the current respiratory infection.

Need for oxygen supplementation [binary]	
Does the subject require any oxygen supplementation (non-invasive or invasive) after first dose of study drug?
 
Categories will be Yes (1) or No (0).
 
Only derive this parameter for subjects that did not require oxygen supplementation before first dose of study drug (no score will be assigned otherwise).
 
If the subject required supplemental oxygen prior to the current respiratory infection, requirement will be defined as having not returned to the level provided prior to the current respiratory infection.

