Time (hours) to end of hydration/feeding supplementation up to 72h from first hospital discharge [time to event]	
Regardless of whether or not the subject is receiving hydration/feeding supplementation at time of first dose of study drug: time (hours) from first dose of study drug to last end date/time of any hydration/feeding supplementation received, but within 72h following first hospital discharge. Excludes hydration/feeding supplementation received during re-hospitalizations that occurred >72 hours after initial hospital discharge
 
Time (hours) will be set to 0h for subjects not requiring hydration/feeding supplementation after first dose of study drug.
 
Censoring will be applied as follows:
	
Situation
 
 
 For subjects with missing data prior to event due to:	Censored at date/time of completion, withdrawal/discontinuation of the study or LTFU accordingly Note: missing time will be imputed as 12:00	
 
 Death (without previous evidence of supplementation end/hospital discharge)	Censored at date/time of death	
 
 
time to event (hours) = (date/time of event or censoring – date/time of first dose of study drug)/3600, rounded to one decimal
	For subjects with missing data prior to event due to:	Censored at date/time of completion, withdrawal/discontinuation of the study or LTFU accordingly Note: missing time will be imputed as 12:00	Death (without previous evidence of supplementation end/hospital discharge)	Censored at date/time of death
For subjects with missing data prior to event due to:	Censored at date/time of completion, withdrawal/discontinuation of the study or LTFU accordingly Note: missing time will be imputed as 12:00					
Death (without previous evidence of supplementation end/hospital discharge)	Censored at date/time of death					

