
Time (hours) to return to pre-RSV disease level for HR: based on investigator evaluation [time to event]
	
Censoring rules and derivation: as for 'Time to return to pre-RSV disease level for RR: based on investigator evaluation'
 
Normalization of HR will be derived from the investigator response to the corresponding question in the Vital Signs eCRF: 'Is this Pulse value normal for this patient?'

Time (hours) to SpO₂ ≥ 92% on room air [time to event]
	
The time from first dose of study drug until the time of first SpO₂ measurement ≥ 92% on room air, and where no supplemental oxygen supplementation is given at or after this timepoint and where no value < 92% are measured after this timepoint.
 
Subjects with SpO₂<92% on room air or who are still on oxygen supplementation at the last SpO₂ assessment will be censored at the date and time of the last SpO₂ assessment.
 
If no oxygen supplementation was necessary post-baseline and the subject had SpO₂ measurement ≥ 92% on room air at baseline and all post-baseline measurements, the value (time to event [hours]) will be set to 0 hours.
 
If the subject required supplemental oxygen prior to the current respiratory infection, end date/time will be defined as the date/time the subject has returned to the level provided prior to the current respiratory infection.
 
time to event (hours) = (date/time of event or censoring – date/time of first dose of study drug)/3600, rounded to one decimal

Table 20: Additional Clinical Course Parameters for Hospitalized Subjects

Time (hours) to $\text{SpO}_2 \geq 95\%$ on room air [time to event]	Censoring rules and derivation: as for 'Time (hours) to $\text{SpO}_2 \geq 92\%$ on room air'

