Time (hours) to clinical stability: protocol definition [time to event]	
Time at which all the following criteria are met:
 
Return to pre-RSV disease status for otherwise healthy subjects and subjects with (a) risk factor(s) for severe RSV disease:
 
 • heart rate AND • respiratory rate AND • blood oxygen level 
AND
 
No more oxygen supplementation for otherwise healthy subjects and subjects with (a) risk factor(s) for severe RSV disease
 
AND
 
No more intravenous (IV)/nasogastric tube feeding/hydration in otherwise healthy subjects or return to pre-RSV status of IV/nasogastric tube feeding/hydration in subjects with (a) risk factor(s) for severe RSV disease
 
Time to clinical stability (protocol definition) will be evaluated using two approaches:
 
The time from first dose of study drug until the time at which each of the following criteria are met (=event):
 
 • Normalization of oxygen supplementation (as in parameter Time [hours] to end of oxygen supplementation up to 72h from first hospital discharge), • Normalization of feeding/hydration (as in parameter Time [hours] to end of hydration/feeding supplementation up to 72h from first hospital discharge), • Normalization of RR (as in parameter Time [hours] to return to pre-RSV disease level for RR: based on investigator evaluation), and • Normalization of HR (as in parameter Time [hours] to return to pre-RSV disease level for HR: based on investigator evaluation), and • Normalization of blood oxygen level (as in parameter Time [hours] to $\text{SpO}_2 \geq 92\%$ on room air) 
The time from first dose of study drug until the time at which each of the following criteria are met (=event):

Table 20: Additional Clinical Course Parameters for Hospitalized Subjects

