Time (hours) to resolution of RSV [summary]	Four summary parameters: 
 • Key RSV symptoms • Respiratory symptoms

Measurement	Formula

parameter]: 24h supplementation free definition [time to event]
	
 General illness behavior Overall RSV symptoms 
In the subset of hospitalized subjects (Cohort 1), time (hours) from first dose of study drug until the date/time of first observed resolution of all individual RSV concepts comprising the relevant summary parameters (refer to Attachment 2 for concepts comprising each RSV summary parameter). Where resolution occurs when ALL criteria, noted below, are met:
 
 All individual RSV concepts comprising relevant summary parameter are scored as 0 (none) or 1 (mild) for approximately 24h AND At least 24h oxygen supplementation free AND At least 24h hydration/feeding supplementation free) 
If caregiver is completing the ObsRO as expected per protocol, the approximate 24h summary score resolution can be defined with the considerations as detailed in Section 5.3.1.2.1.
 
In case not all RSV concepts, comprising a summary parameter, are resolved, data will be censored. Similar rules as for time to resolution of each ObsRO individual symptom (concept) will be applied as described in Section 5.3.1.2.1, such that:
 
time to event (hours) = (date/time of event or censoring – date/time of first dose of study drug)/3600, rounded to one decimal

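### Clinical stability in risk-factor children: the stated feeding criterion is return to pre-RSV status, but the derivation it points to has no such clause

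*SAP*

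**What the plan says.** **Stated feeding criterion.** Section 5 (secondary endpoints, hospitalized subjects) and the Table 20 row on clinical stability by protocol definition agree. Otherwise healthy children must be off IV or nasogastric support. For the others the criterion is "return to pre-RSV status of IV/nasogastric tube feeding/hydration in subjects with (a) risk factor(s) for severe RSV disease".

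**Derived feeding component.** The same Table 20 row takes this component from the time-to-end parameter for hydration/feeding, which uses the "last end date/time of any hydration/feeding supplementation received, but within 72h following first hospital discharge". Children not requiring such support after first dose are set to 0h. If no event is seen, time is censored at completion, withdrawal, loss to follow-up or death. If any of the five components of clinical stability is censored, the composite is censored.

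**Oxygen.** The stated criterion is "No more oxygen supplementation for otherwise healthy subjects and subjects with (a) risk factor(s) for severe RSV disease", and the derivation takes the "last end date/time of any oxygen supplementation received, but within 72h following first hospital discharge". The SpO2 row, another component of the same composite, says that for children on oxygen before this infection the "end date/time will be defined as the date/time the subject has returned to the level provided prior to the current respiratory infection". The row on duration of oxygen says that "the end date/time will be the date/time that the supplemental oxygen administration returned to the level provided prior to the current respiratory infection".

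**Supplementation-free endpoints.** In Section 5.4.1 (Table 22), the 24h definition of resolution requires "At least 24h oxygen supplementation free AND" the same for feeding. The 12h ClinRO definition and the clinically resolved status are equally absolute. None of them mentions support that was in place before RSV.

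**The concern.** The SAP expects some children to have been on oxygen or tube feeding before the infection, because several Table 20 rows carry a clause for them. Presence of risk factors is a randomization stratum and a reported subgroup. If the clause is missing from a component of clinical stability, a child who has fully returned to his or her usual state may not be recorded as stable. To that extent the endpoint would reflect underlying disease rather than recovery from RSV. Programmers would also have to choose among readings of the text that give different times for the same child.

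**Working it through.** The plan gives no figure for this point, so the check sets the texts side by side and then gives a scale by assumption.

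**1. Target against derivation (Table 20 and Section 5)**

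| Component | Stated criterion, risk-factor children | Derivation used | Pre-infection clause in derivation |
|---|---|---|---|
| Feeding/hydration | return to pre-RSV status | last end of any support | no |
| Oxygen support | none | last end of any support | no |
| Blood oxygen | return to pre-RSV status | SpO2 row | yes |

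For feeding, target and derivation disagree. For oxygen support they agree with each other but do not fit the blood oxygen component.

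**2. One child, three possible outcomes.** Take a child who was tube-fed before RSV and returns to the usual feeding level at time R. By the stated criterion, feeding normalizes at R. Under the derivation:
- *One continuing record with no end.* There is no event. The component is censored at study completion, and the composite with it.
- *The 0h rule read with the Table 20 row on requirement for feeding*, where a child at the pre-infection level does not count as requiring support. A child at that level from first dose onward gets 0h, which matches the target. The text does not say that this meaning applies to the 0h rule.
- *Feeds entered as separate records.* The row on duration of feeding describes individual administration records. The last record ending within 72h of discharge could then count as the event. Its time follows from discharge, not from R.

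**3. Oxygen within the composite.** Every component must be met. A child on long-term oxygen may pass the SpO2 component through its clause, but the oxygen component has no clause. The allowance therefore cannot change the composite.

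**4. Scale**

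Inputs from Section 1.4: 144 children in Cohort 1, 48 per arm, placebo median 3 days, scale parameter 1/0.65. The median and scale were set for symptom resolution and serve here only as an illustration. The share f of children who cannot have the event is not in the SAP, so 1% to 10% is assumed.

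Kaplan-Meier plateau: 1/48 = 2.1 percentage points for each child censored at study end.

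Median: solve (1 − f)·F(t) = 0.5 with F log-logistic and median 3, which gives t = 3·[0.5/(0.5 − f)]^σ. Take σ = 0.65 if 1/0.65 is read as the shape, and σ = 1/0.65 if it is read as σ itself.

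| f | children of 144 | median, σ = 0.65 | median, σ = 1/0.65 |
|---|---|---|---|
| 1% | 1.4 | 3.04 days | 3.09 days |
| 2% | 2.9 | 3.08 days | 3.19 days |
| 5% | 7.2 | 3.21 days | 3.53 days |
| 10% | 14.4 | 3.47 days | 4.23 days |

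The factor [0.5/(0.5 − f)]^σ multiplies the median of any arm, so an equal share in each arm leaves the ratio of medians unchanged.

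**The case against.** The strongest reply is that only the feeding mismatch contradicts a stated target. Much of it stands, and it rules out several stronger readings.

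- A reader might infer that these children can never reach stability. Step 2 shows that the text also permits 0h or an event at the last feeding record.
- A reader might infer that the oxygen derivation misses its own target. It does not: Section 5 and Table 20 both ask for no more oxygen, also in risk-factor children. What remains is an inconsistency with the blood oxygen endpoint in Section 5 and with the Table 20 rows on duration of, and need for, oxygen and on SpO2. The SpO2 row is itself not clean. It also requires that no oxygen be given at or after the timepoint, and it censors children still on oxygen. Section 5 limits that endpoint to children not on oxygen before symptom onset.
- A reader might extend the contradiction to the supplementation-free endpoints. No pre-RSV target is stated there, and Section 5.4 explains the rule as avoiding confounding by continued support. It is an omission that does not match the other endpoints. Nor is censoring near Day 28 the rule there: the 24h definition follows the ObsRO diary rules, the 12h definition censors around discharge, and clinically resolved status is a daily yes/no.
- Eligibility and numbers cannot be confirmed from the SAP. Its own clauses show only that such children were expected.

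None of this removes the feeding mismatch.

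**Conclusion.** The point holds for feeding: the stated criterion for risk-factor children is not what the derivation delivers, and the result for an affected child depends on the reading chosen. For oxygen, the components of one composite use different standards and must be reconciled. For the supplementation-free endpoints, the rule for prior support is unstated.

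The size is probably small. It rests on an unknown share of children and concentrates in the risk-factor stratum. The medians above assume that affected children are censored, which is only one of the three readings. A reader might infer a shifted accelerated failure time ratio. The documents do not support that here: Section 5.3.2.3.2 analyses clinical stability and time to end of feeding by Kaplan-Meier only. A shift would also need an assumed imbalance between arms, although randomization is stratified on risk factors.

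**What to change.** 1. In Table 20, add to time to end of hydration/feeding, and to the feeding part of the combined time-to-end row, the clause already used for requirement for feeding, duration of and need for oxygen, and SpO2. If support was needed before the current infection, the end is the date/time of return to the pre-infection level.
2. State whether the 0h rule uses the meaning of requiring support given in the row on requirement for feeding.
3. Reconcile the oxygen criterion of clinical stability and its derivation with the blood oxygen endpoint in Section 5 and with the duration, need and SpO2 rows.
4. State one rule for children on support before RSV in the 24h and 12h supplementation-free definitions and in clinically resolved status.

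Items 1 and 2 cost SAP wording and programming, and the pre-infection level is already needed for other rows. Item 3 concerns a criterion labelled as the protocol definition, so check it against the protocol first; it may not be a SAP-only change. All four should be settled before the final unblinded derivation.
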